10.4.1. Definition of AE

AE Definition

• An AE is any untoward medical occurrence in a clinical study participant, temporally associated with the use of study intervention, whether or not considered related to the study intervention.• NOTE: An AE can therefore be any unfavorable and unintended sign (including an abnormal laboratory finding), symptom, or disease (new or exacerbated) temporally associated with the use of study intervention.

Definition of Unsolicited and Solicited AE

• An unsolicited adverse event is an adverse event that was not solicited using a Participant Diary and that is communicated by a participant who has signed the informed consent. Unsolicited AEs include serious and non-serious AEs.• Potential unsolicited AEs may be medically attended (ie, symptoms or illnesses requiring a hospitalization, or emergency room visit, or visit to/by a health care provider). The participants will be instructed to contact the site as soon as possible to report medically attended event(s), as well as any events that, though not medically attended, are of participant's concern. Detailed information about reported unsolicited AEs will be collected by qualified site personnel and documented in the participant's records.• Unsolicited AEs that are not medically attended nor perceived as a concern by participants will be collected during interview with the participants and by review of available medical records at the next visit.• Solicited AEs are predefined local at the injection site and systemic events for which the participant is specifically questioned, and which are noted by the participant in their diary.

Events to be Collected as AEs

• Any abnormal laboratory test results (hematology, clinical chemistry, or urinalysis) or other safety assessments (eg, ECG, radiological scans, vital signs measurements), including those that worsen from baseline, considered clinically significant in the medical and scientific judgment of the investigator (ie, not related to progression of underlying disease).• Exacerbation of a chronic or intermittent pre-existing condition including either an increase in frequency and/or intensity of the condition.• New conditions detected or diagnosed after study intervention administration even though it may have been present before the start of the study.• Signs, symptoms, or the clinical sequelae of a suspected intervention- intervention interaction.• Signs, symptoms, or the clinical sequelae of a suspected overdose of either study intervention or a concomitant medication. Overdose per se will not be reported as an AE/SAE unless it is an intentional overdose taken with possible suicidal/self-harming intent. Such overdoses should be reported regardless of sequelae.

Events to be Collected as AEs
 
 • “Lack of efficacy” or “failure of expected pharmacological action” per se will not be reported as an AE or SAE. Such instances will be captured in the efficacy assessments. However, the signs, symptoms, and/or clinical sequelae resulting from lack of efficacy will be reported as AE or SAE if they fulfill the definition of an AE or SAE.

Events NOT to be Collected as AEs
 
 • Any clinically significant abnormal laboratory findings or other abnormal safety assessments which are associated with the underlying disease, unless judged by the investigator to be more severe than expected for the participant’s condition. • The disease/disorder being studied or expected progression, signs, or symptoms of the disease/disorder being studied, unless more severe than expected for the participant’s condition. • Medical or surgical procedure (eg, endoscopy, appendectomy): the condition that leads to the procedure is the AE. • Situations in which an untoward medical occurrence did not occur (social and/or convenience admission to a hospital). • Anticipated day-to-day fluctuations of pre-existing disease(s) or condition(s) present or detected at the start of the study that do not worsen.

10.4.2. Definition of SAE

A SAE is defined as any untoward medical occurrence that, at any dose:

1. Results in death

2. Is life-threatening The term “life-threatening” in the definition of “serious” refers to an event in which the participant was at risk of death at the time of the event. It does not refer to an event, which hypothetically might have caused death, if it were more severe.

3. Requires inpatient hospitalization or prolongation of existing hospitalization In general, hospitalization signifies that the participant has been admitted (usually involving at least an overnight stay) at the hospital or emergency ward for observation and/or treatment that would not have been appropriate in the physician’s office or outpatient setting. Complications that occur during hospitalization are AEs. If a complication prolongs hospitalization or fulfills any other seriousness criteria, the event will be considered as serious. When in doubt as to whether “hospitalization” occurred or was necessary, the AE should be considered serious. Hospitalization for elective treatment of a pre-existing condition that did not worsen from baseline will not be collected as an AE.

4. Results in persistent or significant disability/incapacity The term disability means a substantial disruption of a person’s ability to conduct normal life functions. This definition is not intended to include experiences of relatively minor medical significance such as uncomplicated headache, nausea, vomiting, diarrhea, influenza, and accidental trauma

A SAE is defined as any untoward medical occurrence that, at any dose:
(eg, sprained ankle) which may interfere with or prevent everyday life functions but do not constitute a substantial disruption.
5. Is a congenital anomaly/birth defect
6. Other situations: Medical or scientific judgment should be exercised by the investigator in deciding whether SAE reporting is appropriate in other situations such as significant medical events that may jeopardize the participant or may require medical or surgical intervention to prevent 1 of the other outcomes listed in the above definition. These events should usually be considered serious. Examples of such events include invasive or malignant cancers, intensive treatment for allergic bronchospasm, blood dyscrasias, convulsions or development of intervention dependency or intervention abuse.

10.4.3. Recording and Follow-up of AEs and/or SAEs

AE and SAE Recording
When an AE/SAE occurs, it is the responsibility of the investigator to review all documentation (eg, hospital progress notes, laboratory reports, and diagnostics reports) related to the event. The investigator will then record all relevant AE/SAE information. It is not acceptable for the investigator to send photocopies of the participant's medical records in lieu of completion of the required form. There may be instances when copies of medical records for certain cases are requested. In this case, all participant identifiers, with the exception of the participant number, will be redacted on the copies of the medical records before submission. The investigator will attempt to establish a diagnosis of the event based on signs, symptoms, and/or other clinical information. Whenever possible, the diagnosis (not the individual signs/symptoms) will be documented as the AE/SAE.

Assessment of Severity
The investigator will make an assessment of intensity for each AE and SAE reported during the study. All AEs observed will be graded using the National Cancer Institute (NCI) Common Terminology Criteria for Adverse Events (CTCAE) version 5.0. The NCI CTCAE is a descriptive terminology, which can be utilized for AE reporting. A grading (severity) scale is provided for each AE term. The grade refers to the severity of the AE. If a particular AE's severity is not specifically graded by the guidance document, the investigator is to use the general NCI CTCAE definitions of grade 1 through grade 5 following his or her best medical judgment. The CTCAE displays grades 1 through 5 with unique clinical descriptions of severity for each AE based on the following general guideline: Grade 1: Mild; asymptomatic or mild symptoms; clinical or diagnostic observations only; intervention not indicated. Grade 2: Moderate; minimal, local or noninvasive intervention indicated; limiting age-appropriate instrumental activities of daily living.

Grade 3: Severe or medically significant but not immediately life-threatening; hospitalization or prolongation of hospitalization indicated; disabling; limiting self-care activities of daily living.

Grade 4: Life-threatening consequences; urgent intervention indicated.

Grade 5: Death related to AE.

Note: a semi-colon indicates ‘or’ within the description of the grades.

An AE that is assessed as severe should not be confused with an SAE. Severe is a category utilized for rating the intensity of an event; both AEs and SAEs can be assessed as severe. An event is defined as ‘serious’ when it meets at least 1 of the predefined outcomes as described in the definition of an SAE, NOT when it is rated as severe.

Assessment of Causality

The investigator is obligated to assess the relationship between study intervention and each occurrence of each AE/SAE, under 1 of the following categories.

- Not related: Events can be classified as “not related” if there is not a reasonable possibility that the IMP caused the AE.
- Unlikely related: An “unlikely” relationship suggests that only a remote connection exists between the IMP and the reported AE. Other conditions, including chronic illness, progression or expression of the disease state, or reaction to concomitant medication, appear to explain the reported AE.
- Possibly related: A “possible” relationship suggests that the association of the AE with the IMP is unknown; however, the AE is not reasonably supported by other conditions.
- Probably related: A “probable” relationship suggests that a reasonable temporal sequence of the AE with drug administration exists and, in the Investigator’s clinical judgment, it is likely that a causal relationship exists between the drug administration and the AE, and other conditions (concurrent illness, progression or expression of disease state, or concomitant medication reactions) do not appear to explain the AE.
- Related: A “related” relationship suggests that the AE follows a reasonable temporal sequence from administration of IMP, it follows a known or expected response pattern to the IMP, and it cannot reasonably be explained by known characteristics of patient’s clinical state.

A “reasonable possibility” of a relationship conveys that there are facts, evidence, and/or arguments to suggest a causal relationship, rather than a relationship cannot be ruled out.

The investigator will use clinical judgment to determine the relationship.

Alternative causes, such as underlying disease(s), concomitant therapy, and other risk factors, as well as the temporal relationship of the event to study intervention administration will be considered and investigated.

The investigator will also consult the IB and/or Product Information, for marketed products, in his/her assessment.

For each AE/SAE, the investigator must document in the medical notes that he/she has reviewed the AE/SAE and has provided an assessment of causality.

There may be situations in which an SAE has occurred and the investigator has minimal information to include in the initial report. However, it is very important that the investigator always make an assessment of causality for every event before the initial transmission of the SAE data.

Assessment of Causality

The investigator may change his/her opinion of causality in light of follow-up information and send an SAE follow-up report with the updated causality assessment.

The causality assessment is 1 of the criteria used when determining regulatory reporting requirements.

For final reporting purposes, the relationship will be converted into “Binary Determination,” per CIOMS. Unrelated and Unlikely Related will be merged into “Unrelated” and Related, Possibly Related, and Probably Related will be merged into “Related.”

Follow-up of AEs and SAEs

The investigator is obligated to perform or arrange for the conduct of supplemental measurements and/or evaluations as medically indicated or as requested to elucidate the nature and/or causality of the AE or SAE as fully as possible. This may include additional laboratory tests or investigations, histopathological examinations, or consultation with other health care professionals.

If a participant dies during participation in the study or during a recognized follow-up period, the investigator will provide a copy of any post-mortem findings including histopathology.

New or updated information will be recorded in the originally submitted documents.

The investigator will submit any updated SAE data within 24 hours of receipt of the information.

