8.4. Adverse Events and Serious Adverse Events

Definitions of AE and SAE are provided in Section [10.4](#) as well as guidelines for assessing causality and relationship to IMP.

AEs may be reported by the participant (or, when appropriate, by a caregiver, surrogate, or the participant's legally authorized representative).

The investigator and any qualified designees are responsible for detecting, documenting, and recording events that meet the definition of an AE or SAE and remain responsible for following up AEs that are serious, considered related to the trial intervention or trial procedures, or that caused the participant to discontinue IMP and/or the trial (see Section [7](#)).

An unexpected AE is any adverse drug event that is not listed in the reference safety information in the current IB or is not listed at the specificity or intensity that has been observed.

Suspected adverse reaction means any AE for which there is a reasonable possibility that the drug caused the AE.

Each AE is to be evaluated for duration, severity (using the Common Terminology Criteria for Adverse Events [CTCAE Version 5.0]), seriousness, and causal relationship to the IMP or trial procedures. The action taken with the investigational drug and the outcome of the event must also be recorded.

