5. SAFETY ANALYSES

5.1 ADVERSE EVENTS

5.1.1 *Available data*

Adverse events (AEs) are coded into SOC and PT using the latest version of the MedDRA available at the moment of the database lock. For each AE, start and stop date/times are collected as well as severity (NCI CTCAE v5.0), a seriousness flag, treatment relatedness, relatedness to procedures, action taken towards the IMP, outcome, and AE of special interest (AESI) category (infection).

5.1.2 *Derivation rules*

Treatment-emergent adverse events (TEAE) are defined as AEs starting on or after first administration of any IMP up through 60 days after the last administration of the IMP prior to the AE. Post-TEAEs are AEs starting after first administration of IMP that are not TEAEs.

Based on their start date/time, AEs will be allocated to the phase during which they started. Each AE will therefore be reported in only one phase. In case the AE start date/time is incomplete or missing and the AE could consequently be allocated to more than one phase, a worst-case allocation will be done as detailed below:

- Treatment phase vs. non-treatment phase: the AE will be allocated to the treatment phase unless the available parts of the AE start or stop date/time provide evidence for allocating to the non-treatment phase.

A death case is defined as an AE with outcome ‘fatal’.

An AE for which the IMP was discontinued is defined as an AE with action taken ‘drug withdrawn’.

Treatment relatedness will be dichotomized as follows in tables:

- Treatment related: related, probably related, possibly related or missing
- Not treatment related: not related, unlikely related

Adverse events of special interest will be defined using MedDRA system organ class ‘Infections and infestations’.

Injection-related reactions (IRRs) will be defined as all AEs with MedDRA preferred terms that are listed in either:

- Hypersensitivity standardized MedDRA query (SMQ) (broad selection)
- Anaphylactic reaction (SMQ) (broad selection)
- Extravasation events (injections, infusions and implants) (SMQ) (broad selection), excluding implants

AND occurring within 48 hours of an administration, or within 2 days in case no AE start time is available. In case of (partially) missing AE start date, the AE will be considered as an IRR, unless the available parts of the AE start date provide evidence it did not occur within 48 hours of an injection.

	Statistical Analysis Plan	
ARGX-113-1904	Final analysis	Final 2.0 of 22NOV2023

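### The causality scale in Protocol 10.4.3 has no category that clearly fits an event with both a plausible IMP cause and a plausible other cause, and its wording favours 'Unlikely', which is reported as unrelated

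*Protocol*

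**What the plan says.** Protocol 10.4.3 (Assessment of Causality) requires one of five grades for each event.

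- 'Not related' is for events with no reasonable possibility of an IMP cause.
- 'Unlikely related': the "relationship suggests that only a remote connection exists between the IMP and the reported AE". The definition continues: "Other conditions, including chronic illness, progression or expression of the disease state, or reaction to concomitant medication, appear to explain the reported AE".
- 'Possibly related': "the association of the AE with the IMP is unknown; however, the AE is not reasonably supported by other conditions".
- 'Probably related' needs a plausible time course and a likely causal link. It also requires that other conditions (illness, disease state, "concomitant medication reactions) do not appear to explain the AE".
- 'Related' needs a plausible time course, a known or expected response pattern, and that "it cannot reasonably be explained by known characteristics of" the patient's clinical state.

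The five grades then become two. Protocol 10.4.3 states that "Unrelated and Unlikely Related will be merged into" the unrelated class, and the other three form the related class. SAP 5.1.2 makes the same split: "Not treatment related: not related, unlikely related".

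Protocol 8.4 uses a different test: "Suspected adverse reaction means any AE for which there is a reasonable possibility that the drug caused the AE". Section 10.4.3 explains that a reasonable possibility means positive grounds for suspecting causation, which is more than being unable to rule it out. It does not require other causes to be excluded.

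**The concern.** A usual 'possible' grade covers events that the study drug may have caused although something else could also explain them. Here that grade is closed to events that other conditions reasonably support, and the two grades above it carry exclusions of their own. The only grade that admits another explanation is counted as unrelated.

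In this trial a competing explanation for infection is the normal situation. Section 6.8.1 gives oral prednisone to everyone in both arms. Section 8.3.7 names mucosal pemphigus lesions and corticosteroid treatment among the causes of infection. Section 8.4.8 says that the IMP lowers IgG, with a potential infection risk, and makes infections the event of special interest. An infection with two plausible causes is thus an expected event, and the scale does not say how to grade it.

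At stake are the treatment-related safety summaries and the investigator's causality assessment, which 10.4.3 lists as one of the criteria for regulatory reporting. Under-attribution is one risk. Inconsistency is another, because investigators may fill the gap in different ways.

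**Working it through.** No sample size, power or event rate enters this point, so the check is a comparison of texts. Take an infection for which there are positive grounds to suspect the IMP (the connection is not remote) and for which prednisone or pemphigus is an equally plausible cause.

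| Grade | Condition in 10.4.3 | Does the event meet it? | Reported as |
|---|---|---|---|
| Not related | No reasonable possibility of an IMP cause | No: there is one | Unrelated |
| Unlikely | Only a remote IMP connection, and another cause appears to explain the event | Second part yes, first part no | Unrelated |
| Possibly | Not reasonably supported by other conditions | No, if prednisone or pemphigus counts as such a condition | Related |
| Probably | Causal link likely; disease and concomitant medication do not appear to explain the event | No | Related |
| Related | Known or expected response pattern; not reasonably explained by clinical state | Arguable if prednisone is the only rival, since medication is not named; no if pemphigus is the rival | Related |

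No row is clearly met. 'Unlikely' comes nearest for an investigator who starts from the rival cause, because it is the only definition that names disease state and reaction to concomitant medication as reasons for choosing it.

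Now apply the test in 8.4 to the same event. A reasonable possibility exists, so it is a suspected adverse reaction, yet it fails 'Possibly', the lowest grade that counts as related. The two standards disagree on the same event.

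Neither document repairs this elsewhere. Protocol 9.5.5 and SAP 5.1.2 count missing relatedness as related, but a recorded 'Unlikely' is not missing. Section 8.4.4 records relationship to the IMP and to corticosteroids separately, so attribution to both is possible in principle, but the IMP definitions still apply to the IMP field.

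Outputs that depend on the grade, from SAP 5.1.3 and 8.1: Tables 14.3.1.4 (treatment-related TEAEs), 14.3.1.6 (serious), 14.3.1.9 (Grade 3 or more) and 14.3.1.14 (special interest), with the matching rows of the overview tables. The all-causality counterparts, 14.3.1.2, 14.3.1.5, 14.3.1.8 and 14.3.1.13, do not use it.

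The only figures in the documents on this subject are the phase 2 infections in 8.4.8: 7 events probably or possibly related and 25 not or unlikely related, 7 + 25 = 32, so 7/32 = 21.9% were attributed to the drug. The documents do not say that the phase 2 trial used these definitions, so the split is context only.

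**The case against.** The strongest reply is that the text contains no automatic downgrade. Section 10.4.3 leaves the grade to clinical judgment, asks for alternative causes to be considered and investigated, and sends the investigator to the IB. A reader might infer that every infection with two plausible causes is graded 'Unlikely'. The documents do not say so: 'Unlikely' also needs a remote connection, which such an event lacks. This part of the reply stands. The defect is a gap with a lean towards 'Unlikely', and judgment has to be exercised within definitions that do not cover the case.

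The second reply is that the consequences are largely contained, and most of it also stands. SAEs and AESIs go to the sponsor within 24 hours (8.4.1), SAEs regardless of relatedness (8.4.4). The sponsor's designee may make an independent medical assessment (8.4.3), and the sponsor is responsible for SUSAR reporting (8.4.5). The DSMB reviews unblinded safety data (10.1.5.1). Investigators are blinded, so any strictness should fall on both arms alike, and the randomized comparison of all infections does not depend on the grade. These safeguards limit the harm. They do not make the treatment-related tables interpretable or remove the conflict between the two standards.

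**Conclusion.** The point holds as a wording defect with limited reach. The scale lacks a clear category for an event with a plausible IMP cause and a plausible rival cause, it leans towards a grade counted as unrelated, and it disagrees with the reasonable-possibility standard in 8.4 and 10.4.3. The conclusion assumes that prednisone or pemphigus counts as an 'other condition' under 'Possibly related'. The neighbouring definitions, which list disease state and concomitant medication reactions under that term, support this. It should be corrected, but it does not threaten the trial's main safety or efficacy comparisons.

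Three further inferences are tempting, and the documents do not support them.

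- That almost no infection could be graded related. Universal exposure to prednisone does not mean that prednisone explains each infection, and no rate can be derived.
- That the scale contradicts 8.4.8. An AESI is defined there whether related or not, and SAP 5.1.2 identifies AESIs by system organ class, so no infection loses that status.
- That investigators must choose between IMP and prednisone, and so push SAEs into the treatment-failure endpoint. The two relationships are separate fields in 8.4.4, and the grade in one does not set the other.

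**What to change.** In Protocol 10.4.3:

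1. Redefine 'Possibly related' to include events with a reasonable possibility that the IMP contributed, even if the disease or concomitant medication, including prednisone, could also explain them.
2. Limit 'Unlikely related' to events where an IMP contribution is remote, so that another explanation alone is not enough for that grade.
3. Keep the merge into two classes in 10.4.3 and SAP 5.1.2, and keep the separate IMP and corticosteroid fields in 8.4.4.

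The cost is protocol wording and matching guidance for completing the eCRF. The SAP derivation does not change, and no dose, visit or efficacy analysis is affected. The downside is that more events will be classed as related in both arms, so the treatment-related tables will be less specific and should be read against placebo.
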